8.3 Subsequent therapy

A table summarizing the subsequent therapies received after treatment discontinuation will be shown.

Time to first subsequent therapy or death will be analyzed as a measure of the time from first drug administration to treatment failure that leads to the need of a further treatment regimen.

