### **5.2.1.2 Reasons for Treatment Discontinuation**

Patients will receive study treatment until:

- Disease progression (PD).
- Maximum of six cycles unless the patient is in:
  - PR 4–8 weeks after last dose of Cycle 6: in accordance with Investigator decision, the patient may then continue in treatment until CR or progression.
  - SD 4–8 weeks after last dose Cycle 6: in accordance with Investigator decision, the patient may then continue until CR or progression.
- If patient is in CR after six treatment cycles, treatment should be stopped.
- The patient achieves PR or CR at any time during the planned six cycles and is eligible for consolidation with autologous or allogeneic stem cell transplant (SCT) as per Investigator criteria.
- There is unacceptable toxicity.
- There is intercurrent illness of sufficient magnitude to preclude safety continuation of the study.
- There is patient refusal and/or non-compliance with study requirements.
- Investigator's decision.
- There is a protocol deviation with an effect on the risk/benefit ratio management of the patient.
- There is a treatment delay > 15 days from the treatment due date (except in case of clear clinical benefit and with the Sponsor's approval).
- There is a requirement of > 2 dose reductions (except in case of clear clinical benefit and with the Sponsor's approval).

Patients who are withdrawn for any reasons must not be re-treated in the context of this study at any time. For follow-up activities, please refer to Section [5.11](#).

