## 5.7 PATIENT RANDOMIZATION

Not applicable.

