Progression-free survival (PFS) is defined as the time from the date of first administration to the date of documented progressive disease (PD) or death (regardless of the cause of death). If the patient receives further antitumor therapy (including stem cell transplant) before, PFS will be censored on the date of the last disease assessment prior to the administration of this antitumor therapy. If the patient is lost to follow-up for the assessment of progression the PFS will be censored at the date of last valid tumor assessment. If the patient does not received any drug infusion, he/she will be censored at time zero. Both, independent central review and investigator assessments, will be used for the determination of PFS.

Progression-free survival at 6/12 months (PFS6/PFS12), defined as the Kaplan-Meier estimate of the percentage of patients who are progression-free at six/twelve months after first administration; both independent central review and investigator assessment will be used for the determination of PFS.

Within-patient PFS/TTP, defined as the ratio of the PFS achieved with the experimental treatment versus prior last TTP. Intra-patient PFS/TTP ratio will be categorized and analyzed as a dichotomous variable. Clinical benefit will be defined if a >33% longer PFS/TTP with the experimental treatment vs. the TTP with the immediate prior chemotherapy (ratio >1.33) is achieved.

Overall survival (OS), defined as the time from the date of first administration to the date of death (of any cause) or last patient contact.

Overall survival at 6/12 months (OS6/OS12), defined as the Kaplan-Meier estimate of the percentage of patients who are alive at six/twelve months after first administration.

Treatment safety [AEs, serious adverse events (SAEs) and laboratory abnormalities] graded according to the NCI-CTCAE, v. 4. Dose reductions, skipped doses or dose delays required due to treatment-related AEs, and reasons for treatment discontinuations will be analyzed.

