10.2 Reasons for treatment discontinuation

Table 10.2.1 Treatment discontinuation

	N	%
Progressive disease	X	X.X
Treatment related adverse event		
Non treatment related adverse event		
Patient refusal to treatment		
Investigator decision		
Death (due to toxicity)*		
Death (non-treatment-related)**		
Complete response		
PR or CR and eligible for consolidation with autologous or allogeneic SCT		
Other ***		
Total		

(*) Cause of death = study drug related (**) Cause of death = Malignant disease / non study drug related / Other (***) Specify (see listing 10.2.2). Patients included but not treated will not be shown in this table.

When reason for discontinuation is toxicity or study treatment-related death, identify patients and describe them in depth here.

Listing 10.2.2 Reasons for treatment discontinuation other than progressive disease.

Patient id.	Reason	Last cycle	Comments

Listing 10.2.3 Treatment discontinuation due to AEs

Patient id.	Cycle	Preferred term code	Adverse event reported (verbatim)	Grade	Relationship	Onset date	Resolved date	Significant consequences

Table 10.2.4 Study discontinuation

	N	%
Study termination (clinical cut-off)	X	X.X
Patient's refusal		
Never treated*		
Death (due to toxicity)**		
Death (non-treatment-related)***		
Investigator decision		
Patient's follow-up completed		
Lost to follow-up		
Other ****		
Total		

(*) See Listing 10.2.6 (**) Cause of death = study drug related (***) Cause of death = Malignant disease / non study drug related / Other (****)See Listing 10.2.5

Listing 10.2.5 Study discontinuation due to other reason

Patient id.	Specify

Listing 10.2.6 Patients included but not treated

Patient id.	Off-study reason

Listing 10.2.7 Patients included without AITL diagnosis confirmed after central pathological review

Patient id.	Treated (Y/N)

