12.5.2 LVEF, ECG and other related tests

Listing 12.5.2.1 Electrocardiogram results. Evolution during the study.

Patient id.	Cycle	ECG result

Listing 12.5.2.2 LVEF evolution during the study.

Patient id.	LVEF(%)		
	Baseline*	Minimum*	End of treatment*
	X.X	X.X	X.X
Median(Range)	X.X (X.X-X.X)	X.X (X.X-X.X)	X.X (X.X-X.X)

(*) LVEF (%) value and method

Listing 12.5.2.3 Median change in LVEF.

Cycles	LVEF
Baseline	X.X (X.X-X.X)
Minimum	X.X (X.X-X.X)
End of treatment	X.X (X.X-X.X)

12.6 Concomitant therapy / procedures according to the ATC classification.

Table 12.6.1 Concomitant medication during treatment (ATC levels)

Medication Term (ATC level 1)	Medication Term (ATC level 2)	Medication Term (ATC level 4)	Preferred Name		
				N	%
				X	X.X

Listing 12.6.2 Patients with EPO or G-CSF.

Patient id.	Type	Route	Dose	Unit	Start date	Stop date	Reason	Indication

Listing 12.6.3 Patients with any transfusion during treatment

Patient	Cycle	Date	Blodd product	Specify	Total units	Irradiated

Taken from concomitant therapy dataset.

Table 12.6.4 G-CSF, transfusions or EPO during treatment

	N	%
G-CSF	X	X.X
Platelets transfusions		
Packed red cells transfusions		
Plasma transfusions		
Cryoprecipitates		
Clotting factors		
EPO		

Table 12.6.5 Subsequent therapy

	N	%
Type	X	X.X
Chemotherapy		
...		
Subsequent chemotherapy agents (ATC)		
...		
...		

Table 12.6.6 Time to subsequent therapy or death

	Arm A	Arm B	Parameter	p-value
N				
Events				
Censored				
Time to subsequent therapy or death			Log-Rank: HR (95% CI) :	LR: HR:

Kaplan-Meier plot will be also shown (Figure 12.6.7)

12.7 Safety analysis in special subgroups.

Table 12.7.1 Worst grade 3-4 by patient in special subgroups (Gender)

	Male			Female		
	N	Grade 3-4	%	N	Grade 3-4	%
Thrombocytopenia	X	X	X.X	X	X	X.X
Neutropenia						
ALP						
Total bilirubin						
AST						
ALT						
CPK						
Nausea						
Vomiting						
Fatigue						
Other*						

(*)Any treatment-related toxicity present in >=5% of patients in any group

Table 12.7.2 Worst grade 3-4 by patient in special subgroups (Race)

	White			Other		
	N	Grade 3-4	%	N	Grade 3-4	%
Thrombocytopenia	X	X	X.X	X	X	X.X
Neutropenia						
ALP						
Total bilirubin						
AST						
ALT						
CPK						
Nausea						
Vomiting						
Fatigue						
Other*						

(*)Any treatment-related toxicity present in >=5% of patients in any group

Table 12.7.3 Worst grade 3-4 by patient in special subgroups (Age)

	<65 years old			≥65 years old		
	N	Grade 3-4	%	N	Grade 3-4	%

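### SAP 8.3 makes first subsequent therapy a treatment-failure event without exempting transplant consolidation in responders, and its only table shell is a two-arm comparison in a single-arm trial

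*SAP*

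**What the plan says.** - **Definition.** SAP 8.3 (Subsequent therapy): "Time to first subsequent therapy or death will be analyzed as a measure of the time from first drug administration to treatment failure". The sentence goes on to describe this as "treatment failure that leads to the need of a further treatment regimen". Subsequent therapy is not defined and no therapy is excluded.
- **Transplant as a reason to stop.** Protocol 5.2.1.2 ends study treatment for anyone who "achieves PR or CR at any time during the planned six cycles and is eligible for consolidation with autologous or allogeneic stem cell transplant". SAP Table 10.2.1 gives these patients a separate row, "PR or CR and eligible for consolidation with autologous or allogeneic SCT", apart from progression, adverse events and death.
- **Transplant in PFS and DoR.** SAP 6.1.2: "If the patient receives further antitumor therapy (including stem cell transplant) before, PFS will be censored", with the censoring date set at the last disease assessment before that therapy. DoR uses the same censoring rules.
- **Output.** The shell is "Table 12.6.6 Time to subsequent therapy or death" (SAP Appendix I, section 12.6). Its columns are Arm A, Arm B, a parameter column and a p-value. The rows are N, events, censored and the time itself, with a log-rank test and a hazard ratio with 95% CI. A Kaplan-Meier figure is announced beneath it.
- **Design.** All 60 patients receive plitidepsin (SAP 2). Protocol 5.7, on randomization, reads "Not applicable".
- **Status.** SAP 6.2.2 treats time-to-event endpoints as exploratory. This measure appears in SAP section 8, among other analyses, and not in the endpoint list of SAP 3.3.

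**The concern.** Two things look wrong.

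First, the plan gives one clinical course two opposite meanings. Stopping in remission to have a transplant is recorded in its own disposition category and leaves PFS by censoring. The 8.3 analysis has no matching exemption, so the same transplant would be scored as failure of plitidepsin. The measure would then be shortened by patients who responded. That matters because this is the planned output that follows patients who move to other treatment without a recorded progression, which is where PFS stops looking.

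Second, the shell asks for a comparison between arms that do not exist and names no single-arm summary statistic. The DoR, PFS and OS shells (Tables 11.3.2.18, 11.3.2.22 and 11.3.2.41, for example) are correctly single-column and name a median.

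At stake is whether an exploratory time-to-event result can be interpreted. The trial's success rule is not affected.

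**Working it through.** The plan states no sample size, event target or power for this analysis, so there is no figure to reproduce.

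**1. One patient through the rules.** Take a patient in CR who stops plitidepsin and has a consolidation transplant without progression.

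| Place | Treatment of this patient |
|---|---|
| SAP Table 10.2.1 | Own row, separate from progression, toxicity and death |
| SAP 6.1.2, PFS | Censored at last assessment before SCT |
| SAP 6.1.2, DoR | Same censoring rules as PFS |
| SAP 8.3 | No exemption; first subsequent therapy, so an event described as failure |

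The last row is an inference. It joins the absence of an exclusion in 8.3 to the classification of SCT as antitumor therapy in 6.1.2.

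**2. Effect of each transplant.** 1/60 = 1.7 percentage points off the failure-free proportion from the transplant date. This is a maximum: it is zero at any time by which that patient would have had another event anyway.

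**3. Illustrative number of patients.** The documents give no share of responders going to SCT; 10% to 50% is assumed. Responders: 19 of 60 (the success threshold, 31.7%) up to 60 × 0.41 = 24.6 (the alternative in SAP 5).

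- Low end: 19 × 0.10 = 1.9 patients, 1.9/60 = 3.2%.
- High end: 24.6 × 0.50 = 12.3 patients, 12.3/60 = 20.5%.

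**4. Illustrative effect on the 6-month estimate.** Assumptions, none from the documents except the ORR of 31.7%: exponential times with median 14 months in responders and 2 months in non-responders; a share s of responders selected for SCT at 3 to 6 months.

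- Non-responders event-free at 6 months: 0.683 × 2^(−6/2) = 0.683 × 0.125 = 0.0854.
- Responders event-free at 6 months, ignoring SCT: 0.317 × 2^(−6/14) = 0.317 × 0.743 = 0.2355.
- SCT ignored: 0.0854 + 0.2355 = 0.321.
- SCT as event: 0.0854 + 0.2355 × (1 − s).
- SCT censored: by simulation.

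| s | SCT as event | SCT censored at SCT | SCT ignored |
|---|---|---|---|
| 10% | 29.7% | 31.8% | 32.1% |
| 25% | 26.2% | 31.3% | 32.1% |
| 50% | 20.3% | 30.1% | 32.1% |

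The direction is fixed: counting SCT as an event can only lower the estimate, and the loss comes entirely from responders. The censored column falls slightly below the ignored column because only responders are censored, so that censoring is informative.

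**5. The shell.** In a log-rank test with one group, the expected events at each event time are d × n/n = d, equal to the observed, and the variance carries the factor (n/n)(1 − n/n) = 0. The statistic is 0/0. A hazard ratio needs a second group. The same shows in the Schoenfeld formula, where required events are proportional to 1/[a(1 − a)]: with allocation a = 1 the denominator is zero.

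| Cell in Table 12.6.6 | One arm |
|---|---|
| N, events, censored | Can be filled |
| Kaplan-Meier figure | Can be drawn |
| Second arm column | Empty |
| Log-rank, HR with CI, p-value | Cannot be computed |
| Median with 95% CI | Not named |

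**The case against.** The strongest reply is that 8.3 never mentions transplant and does not say that every therapy counts. Its closing clause refers to failure that creates a need for further treatment, and elective consolidation of a responder is not that. The link to SCT comes from a PFS censoring rule that uses a different term for a different endpoint. This stands in part. The clause allows that reading, so a reader who infers that the SAP expressly scores transplanted responders as failures goes further than the text. But no rule puts the narrower reading into effect, and a programmer working from 8.3 and 6.1.2 together would count the transplant.

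On the shell, a reader might infer that the output cannot be produced at all. That is too strong: the counts and the Kaplan-Meier plot can be. The comparison cells look like a leftover template. They are still wrong as written.

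On size, the documents give some reason to expect few transplants. AITL mainly affects people aged 60 to 80 (Protocol 1.1.1). The three earlier AITL responses lasted 121, 12 and 4 weeks, and both patients with CR had already failed transplant-supported chemotherapy (SAP 1). Table 12.6.5 also shows subsequent therapies by type, so part of the problem would be visible. All of this stands and limits the importance of the point.

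Finally, counting SCT as an event, censoring it and ignoring it answer different questions. Ignoring it credits transplant benefit to plitidepsin. That also stands: the defect is the missing rule and the failure label, and no single handling is the only correct one.

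**Conclusion.** The point holds in two parts. The two-arm comparison in Table 12.6.6 is an error on the face of the document. The transplant problem is a gap: on the natural reading, SAP 8.3 scores a responder taken to consolidation SCT as a treatment failure while PFS and DoR censor the same patient, and nothing in the SAP resolves this.

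The importance is modest. The analysis is exploratory, is not a listed endpoint, and has no bearing on the primary ORR test or the sample size. Only the bound of 1.7 points per transplant in 60 patients follows without assuming a transplant rate. A reader might take the 26.2% against 32.1% above as an expected bias. It is not: it rests on an assumed 25% transplant share and assumed event-time medians.

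Two further inferences are not supported. Transplant is not part of study treatment; the protocol lists it as a reason to stop, at the investigator's judgement. And the row in Table 10.2.1 does not identify transplanted patients. It records eligibility when treatment stopped, and a patient who stopped for CR may sit under the separate complete-response row and be transplanted later.

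**What to change.** 1. **Table 12.6.6.** Replace it with one column: N; events by type (SCT as consolidation in PR/CR, other subsequent therapy, death); censored; Kaplan-Meier median with 95% CI. Delete the second arm and the log-rank, HR and p-value cells.
2. **SAP 8.3.** Define subsequent therapy. Do not label SCT given as consolidation in PR/CR a treatment failure. Report the estimate both with that SCT counted as an event and with it not counted, and state in advance which is the main version. In the not-counted version, censor at SCT, or follow the patient to later therapy or death if later lines are recorded. Different wording would also avoid a clash with SAP 4.1, where treatment failures means certain toxicity discontinuations.
3. **Identification.** Use post-treatment therapy records (SAP section 13, Listings 13.1.36 to 13.1.38) with response status, not Table 10.2.1 alone.

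**Cost.** SAP wording, one table shell and one extra exploratory estimate. Check the CRF first: the post-treatment listings name medical treatment, surgery and radiotherapy but no transplant or consolidation field, and after a new antitumor therapy Protocol 5.11 specifies survival follow-up, so later lines may not be captured. If they are not, showing SCT as its own event type still makes the result readable. The not-counted version has its own weakness: following on may credit transplant benefit to plitidepsin, and censoring at SCT may be informative. Both limitations should be stated with the result.

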8.4 Protocol deviations

Analysis of inclusion/exclusion criteria deviations, retreatment restrictions, used concomitant medication and clinically relevant discontinuations will be done as described in Appendix I.

8.5 Pharmacokinetic and biomarkers analyses

These analyses will be detailed in separate documents.

8.6 Imputation of incomplete dates

The dates of certain historical or current clinical activities are key component for statistical analysis. Incomplete date appears when day, month or year is/are missing, and it could be imputed so that variables like time to and duration of certain event can be calculated. If none of day, month and year is available, then the date is missing, no imputation will be done.

Before treatment start date

If day of a date is unknown then the imputed day will be 15, if the month is also unknown then the imputed date will be July 1st. This assumption will be valid if the imputed date is earlier than the treatment start date; otherwise the imputed date will be the first day of the treatment start month.

Between treatment start and end of treatment

All date variables during treatment where information is needed and is not fully available, for example adverse events or concomitant medications, will be subject of imputation by means of SAS programming. If the day of a date is unknown then the imputed day will be 1, if the month and/or year is also unknown then the imputed date will 1/January. This assumption will be valid if the imputed date is earlier than the treatment start date; otherwise, the imputed date will be the treatment start date.

After end of treatment

To ensure the most conservative approach for the main time-to-event variables (i.e. PFS and OS) that can be affected by missing values the following rules will be implemented by means of SAS programming: if the day of a date is unknown then the imputed day will be 1; if the month is also unknown, then the imputed date will be 1/July. This assumption will be valid if the imputed date occurs later than the last drug administration date; otherwise, the imputed date will be the last drug administration date plus 1 day.

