7.1 Toxicity and adverse events

All the adverse events will be coded using the Medical Dictionary for Regulatory Activities (MedDRA).

The toxicity evaluation will be coded with the National Cancer Institute-Common Terminology Criteria for Adverse Events (NCI-CTCAE), version 4.

As far as all the toxicities are concerned, the NCI-CTCAE grade will be used wherever an NCI-CTCAE grading exists. Otherwise, the severity will be noted. As a convention, the term «Grade» will always be used. Toxicities will be described according to the worst NCI-CTCAE grade or, for toxicities which do not form the subject of NCI-CTCAE classification, according to the worst severity. For “Worst per cycle” calculation purpose, onset and end cycle of each event will be derived.

Summary of overall adverse events will be done by body system and preferred term, by severity (worst toxicity grade) and by relationship to the study drug. Events with unknown relationship will be considered as related events for reporting purposes.

A frequency table will be made for the AEs leading to cycle delay, dose reduction, skipped dose, or withdrawal of study medication. Adverse events with outcome of death will also be presented by relationship to the study drug.

All events entered in Adverse Event form with the onset date before the first drug administration, will be reported as Signs and symptoms. Only those events with start date after/equal the first infusion date will be included in AE tables in Safety section (except those including evolution from baseline).

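### SAP 8.6 has no separate imputation rule for stop dates, so an adverse event with an unknown resolution day can be given an end date before its known onset, even once the comparison with treatment start is corrected

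*SAP*

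**What the plan says.** SAP 8.6 divides partial dates by period. The paragraph on dates between treatment start and end of treatment, which are imputed by a SAS program, opens with its scope: "All date variables during treatment where information is needed and is not fully available, for example adverse events or concomitant medications, will be subject of". The rule is: "If the day of a date is unknown then the imputed day will be 1, if the month and/or year is also unknown", the date becomes 1 January. A condition follows: "This assumption will be valid if the imputed date is earlier than the treatment start date". When the condition fails, the fallback is this: "otherwise, the imputed date will be the treatment start date".

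Onset and resolution dates are treated alike. No sentence compares an imputed stop date with the start date of the same event. The section's stated purpose is that "variables like time to and duration of certain event can be calculated".

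SAP 7.1 relies on these dates. For the worst-grade-per-cycle displays it says that "onset and end cycle of each event will be derived". It does not say what happens if the end cycle comes out before the onset cycle. Entry to the AE tables depends on the event's start date relative to first infusion, not on its stop date.

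**The concern.** The first of the month is the earliest date compatible with a missing day. That is a usable default for an onset. For a resolution it is the early extreme, and it can fall before the event began.

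The same paragraph has another fault: its condition keeps the imputed date only when that date precedes treatment start, which looks like the reverse of what was meant. The two faults need separating. A sponsor who repairs only the comparison would still have stop dates set to the first of the month.

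At stake are AE durations and the outputs built from onset and end cycle: Tables 12.2.1.4, 12.2.1.6, 12.3.1.2 and 12.3.1.4, and Listings 12.2.1.8 and 12.2.1.10. Under either reading the imputed stop is never later than the true on-treatment stop. Any error in the by-cycle counts from this source is therefore an understatement.

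**Working it through.** The documents give no figure on this point, so there is none to reproduce. The check applies the written rule to calendar dates.

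**Inputs from the SAP.** Day = 1 for a missing day, and the treatment-start condition (8.6). Onset and end cycle derived for each event (7.1). Four-week cycles (8.2, stated there for treatment administration and applied here to AEs as an assumption).

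**Assumptions not in the documents.** First doses spread over one calendar year. Onset known and falling on days 0–167, that is, six 28-day cycles. Stop month known, stop day missing. True durations as listed below.

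**One patient.** First dose 10 March, onset 12 May. Cycle number = floor(days since first dose / 28) + 1. Onset is 63 days after first dose: floor(63/28) + 1 = cycle 3.

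- Stop recorded as May, day unknown, comparison corrected: 1 May, 11 days before onset. Day 52: floor(52/28) + 1 = cycle 2, before the onset cycle.
- Stop recorded as June, day unknown, comparison corrected: 1 June, after onset. Day 83: floor(83/28) + 1 = cycle 3. Cycle 4 begins on day 84, 2 June, so if the event really lasted to 2 June or later, its presence in cycle 4 is lost.
- Either stop under the rule as printed: 10 March, 63 days before onset, cycle 1.

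**When the order reverses.** With the comparison corrected, the stop precedes onset when the event resolves in its onset month and began after the 1st (in the month of first dose, after the day of first dose). If it resolves in a later month, the duration is shortened, or unchanged if it resolved on the 1st.

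**Approximate share.** For day = 1 alone, with onset uniform over a 30.4-day month and duration d days, the share is 1 − d/30.4 − 1/30.4. The last term removes onsets on the 1st.

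- d = 7: 1 − 8/30.4 = 0.74
- d = 14: 1 − 15/30.4 = 0.51
- d = 28: 1 − 29/30.4 = 0.05

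**Enumeration over all assumed dates.**

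| True duration (days) | Stop before onset, comparison corrected | End cycle before onset cycle, comparison corrected | Stop before onset, as printed |
|---|---|---|---|
| 7 | 73% | 26% | over 99% |
| 14 | 50% | 12% | over 99% |
| 28 | 5% | 0.2% | over 99% |
| 56 | 0% | 0% | over 99% |

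The enumeration agrees with the formula to within a point. The cycle column is much smaller than the date column because many reversals stay inside one 28-day cycle. As printed, the end cycle precedes the onset cycle in 83–91% across durations of 1 to 56 days.

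**The case against.** The strongest reply is that little depends on these dates. The number of partial stop dates is not given and may be small. Worst-grade-by-patient tables (12.2.1.3, 12.2.1.5, 12.3.1.1, 12.3.1.3) and the summary Table 12.2.1.1 do not use stop dates. Laboratory toxicity is graded from laboratory results, and response is untouched. All of that stands, and it limits the point to AE durations and the by-cycle AE displays.

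It can also be said that the near-universal reversal comes from the printed comparison, not from day 1. That is right, and it is why the figures are given separately. It does not answer the point, because the reversals in the corrected-comparison columns remain after that repair.

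A reader might infer that every event with an unknown resolution day ends before it begins. Once the comparison is corrected, that happens only under the same-month condition above. A reader might also infer that such events drop out of the by-cycle tables. The documents do not say so: entry is by start date, and handling of an end cycle that precedes the onset cycle is unspecified. A program could lose the event, count it in its onset cycle or raise a query.

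**Conclusion.** The rule is wrong as written for stop dates, and correcting the comparison alone does not put it right. Among events with a known onset and an unknown stop day, and with the comparison corrected, the stop precedes onset in roughly three quarters of 7-day events, half of 14-day events and one in twenty 28-day events. The end cycle precedes the onset cycle in about 26%, 12% and 0.2%. These shares depend on the assumed first-dose dates, onset days and durations. They apply only to partial stop dates, so no effect on the trial's overall AE counts can be stated.

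The by-cycle outputs can miss cycles in which an event was present, both through reversed order and through shortening. A general undercount of toxicity is not shown, since the by-patient AE tables are unaffected. The point merits a correction to the SAP but does not bear on the primary endpoint.

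**What to change.** Rewrite the on-treatment paragraph of SAP 8.6 once, together with the correction of the comparison:

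- **Start dates:** keep day 1, but not before first infusion.
- **AE and concomitant-medication stop dates:** use the last day of the known month, or 31 December if only the year is known, and never a date before the event's own start.
- **Cap:** death or data cutoff. Apply the end of AE collection as a further cap only to events not followed beyond it, because Protocol 8.6.1 requires drug-related events to be followed until they resolve or stabilize.
- **SAP 7.1:** state that imputed dates feed the onset and end cycle, and that every event counts at least in its onset cycle.

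The cost is a few sentences and a small change to the date program. The drawback is real: durations can be overstated. On the same assumed dates, month-end imputation before any cap moves the end into a later cycle than the true one in about 52% of such events. A missing month can add many months. That error is in the conservative direction for safety, and the caps limit it.

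### SAP 8.6 reverses the date check for on-treatment imputation, so partially dated adverse events land on or before Cycle 1 Day 1

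*SAP*

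**What the plan says.** SAP 8.6 (Imputation of incomplete dates) has three paragraphs, one per period. The middle one, for dates between treatment start and end of treatment, covers "All date variables during treatment where information is needed and is not fully available, for example adverse events or concomitant medications". It sets a missing day to the first of the month. Where the month or the year is missing as well, "then the imputed date will 1/January". It goes on to state when the result stands: "valid if the imputed date is earlier than the treatment start date; otherwise, the imputed date will be the treatment start date".

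The neighbouring paragraphs use conditions that fit their own periods. Before treatment, an imputed date is kept if it precedes treatment start; if not, "otherwise the imputed date will be the first day of the treatment start month". After treatment: "This assumption will be valid if the imputed date occurs later than the last drug administration date".

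SAP 7.1 (Toxicity and adverse events) makes the safety tables depend on these dates. For entries dated too early it says: "All events entered in Adverse Event form with the onset date before the first drug administration, will be reported as Signs and symptoms". The matching rule on what the safety tables may contain reads: "Only those events with start date after/equal the first infusion date will be included in AE tables in Safety section". Tables of evolution from baseline are exempt. The same section says that the cycle in which each event starts and ends will be derived for the worst-grade-per-cycle displays.

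**The concern.** A date known to fall during treatment cannot precede treatment start, so the check should catch imputed dates that are too early and lift them to the first dose. The text does the reverse. It keeps a date that is impossible for the period and overwrites one that is possible.

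Two errors would follow. A later-cycle event with an unknown day would be assigned to Cycle 1 Day 1. An event in the month of first dose would be dated before that dose and leave the adverse event tables. Safety is a secondary endpoint (SAP 3.3), and this single-arm trial has no control group in which such a dating artefact might show up. Concomitant medications are under the same rule, so the split between baseline use (Table 11.1.11.1) and use during treatment (Table 12.6.1) is exposed too.

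**Working it through.** The documents give no figure to reproduce, so the check applies the rule as written.

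**Notation.** Let *s* be the date of first dose, *i* the imputed date (first of the known month, or 1 January of the known year) and *t* the true onset, with *t* ≥ *s* for an on-treatment event.

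- As written: return *i* if *i* < *s*, otherwise *s*. That is min(*i*, *s*).
- Condition reversed: return *i* if *i* ≥ *s*, otherwise *s*. That is max(*i*, *s*).

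Since min(*i*, *s*) ≤ *s* always, the written rule cannot return a date after first dose. Because *i* is the first day of the month or year containing *t*, *i* ≤ *t*, and so max(*i*, *s*) ≤ *t*. The reversed rule is therefore never further from the true onset than the written one. The two agree only when *i* = *s*, that is, when dosing began on the very date imputed.

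**First dose on 10 March.**

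- Onset June, day unknown: *i* = 1 June, not before *s*, so it is reset to 10 March. The gap is 21 + 30 + 31 + 1 = 83 days.
- Onset March, day unknown, during treatment: *i* = 1 March, before *s*, so it is kept. That is 10 − 1 = 9 days before first dose, and SAP 7.1 makes it a baseline sign or symptom.

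**First dose on 20 June 2016.**

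| Recorded onset | Imputed | As written | Where it is reported | Condition reversed |
|---|---|---|---|---|
| June 2016 | 1 Jun 2016 | 1 Jun 2016 | Signs and symptoms | 20 Jun 2016 |
| September 2016 | 1 Sep 2016 | 20 Jun 2016 | AE tables, Cycle 1 Day 1 | 1 Sep 2016 |
| 2016 only | 1 Jan 2016 | 1 Jan 2016 | Signs and symptoms | 20 Jun 2016 |
| 2017 only | 1 Jan 2017 | 20 Jun 2016 | AE tables, Cycle 1 Day 1 | 1 Jan 2017 |

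**Enumeration.** The assumptions are six 28-day cycles with the last dose 5 × 28 + 14 = 154 days after the first, plus 30 days, so onset offsets run from 0 to 184. Every start date in a 365-day year and every offset are weighted equally, giving 365 × 185 = 67,525 combinations.

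| Missing part | Rule | Before first dose | On first dose | After first dose | Mean absolute error |
|---|---|---|---|---|---|
| Day | As written | 8.0% | 92.0% | 0% | 92.8 days |
| Day | Reversed | 0% | 8.5% | 91.5% | 13.9 days |
| Day and month | As written | 74.5% | 25.5% | 0% | 197.6 days |
| Day and month | Reversed | 0% | 74.8% | 25.2% | 76.4 days |

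The two rules agree in 92.04% − 91.50% = 0.54% of the day-missing combinations and in 25.48% − 25.21% = 0.27% of those with the month missing too. The percentages depend on the uniform grid. The 0% after first dose does not.

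**The case against.** The best case against concedes the reversal and disputes how much it matters.

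- **It looks like a copying slip.** The condition repeats the one in the pre-treatment paragraph, and the fallback makes sense only as a floor, so a programmer may well code the sensible direction. That is plausible, but the SAP does not authorise it. The programmer must either follow a wrong rule or depart from the plan without a record.
- **Moving an event to Cycle 1 Day 1 keeps it in the per-patient tables.** This stands. Tables 12.2.1.1, 12.2.1.3, 12.2.1.5, 12.3.1.1 and 12.3.1.3 are not altered by that shift. The harm is confined to by-cycle output such as Tables 12.2.1.4, 12.2.1.6, 12.3.1.2 and 12.3.1.4, assuming that the cycle is derived from the imputed date, which SAP 7.1 does not spell out.
- **No planned table summarises adverse event duration.** This stands too. The planned duration summaries (Tables 12.4.4.4 and 12.4.4.5) concern laboratory abnormalities.
- **Events dated before first dose are reclassified, not deleted.** Correct: they remain in Table 11.1.10.2 and Listings 11.1.10.3 and 13.1.27. Treatment-emergent events would still be undercounted in the adverse event tables.
- **A start-month onset may truly precede the first dose.** For some records, yes; the partial date alone cannot settle it. But the paragraph governs dates taken to be during treatment, and for those a result before first dose is wrong by definition.
- **The number of partial dates is unknown.** This stands. Adverse events are reported at least every cycle (Protocol 5.8), and nothing suggests that partial dates would be common.

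**Conclusion.** The rule is wrong as written, and no other section corrects it. It cannot produce a date after first dose, although it exists to date events during treatment. Among partial dates it gives the sensible result only when the imputed date coincides with first dose, about 0.5% or less of combinations on the assumed grid.

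The two consequences should be kept apart. With only the day missing, most affected events (92.0% on that grid) are placed on Cycle 1 Day 1 and distort by-cycle output only. A smaller share (8.0%) leaves the adverse event tables. With the month also missing, the share leaving rises to 74.5%.

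The absolute effect on the safety results depends on how many dates are partial, which the documents do not say. Dates missing in full are not imputed. The response rate by independent review, the futility rules and the criterion of 19 responders in 60 do not use this rule.

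**What to change.** In the middle paragraph of SAP 8.6, replace the condition with: *keep the imputed date when it falls on or after the first-dose date; when it falls before, use the first-dose date.* Change the corresponding program line.

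Two gaps in the same paragraph should be closed at the same time:

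- **Stop dates.** As written, every partial stop date lands on or before first dose, so an event could end before it began. The corrected onset rule can still put a stop date before its onset when both fall in the same month. Stop dates need a separate sentence that at least prevents this.
- **Unknown year.** The text gives 1 January without saying of which year. State the year or leave such dates unimputed.

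The cost is one reworded clause, two short additions and the matching program edits. No data collection, design feature or efficacy analysis changes. If any safety output has already been programmed, check which direction was coded and record it.
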